7.4 Analysis of Efficacy

Efficacy analysis will be conducted on the ITT. The interpretation of results from statistical tests will be based on the ITT.

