7.4.2 Analysis of Secondary Endpoints

7.4.2.1 Time to PSA Progression with 1st Line AAT + 2nd Line AAT (TTPP2)

TTPP2 is defined as the period from Day 1 of 2nd line AAT to the date of PSA progression with 2nd line AAT. The total of time to PSA progression with 1st line AAT and time to PSA progression with 2nd line AAT will be evaluated. Convention of censoring is specified in Section 7.10.

The distribution of the TTPP2 will be estimated using the Kaplan–Meier method. The median TTPP2 will be estimated using the 50 percentile value of the Kaplan–Meier curve. The two-sided 95% CI will be calculated based on the estimation. The benefit of enzalutamide as compared to flutamide will be descriptively assessed.

7.4.2.2 PSA Response Rate to 1st Line AAT (Decrease by at Least 50% or 90% from Baseline)

The PSA response rate decreasing by at least 50% will be calculated by treatment groups of subjects with baseline PSA value and PSA measured at least once after baseline. For the comparison of the response rate between the enzalutamide and flutamide groups, the stratified Cochran–Mantel–Haenszel test will be used. The stratification factor will be the disease stages (M0/N0, M0/N1, or M1) used as stratification factor for allocation.

PSA decrease by at least 90% will also be compared at the 0.05 significance level (twosided) between the enzalutamide and flutamide groups using the stratified Cochran–Mantel– Haenszel test.

7.4.2.3 PSA Response Rate to 1st Line AAT at Week 13 (Decrease by at Least 50% or 90% from Baseline)

The PSA response rate decreasing by at least 50% (or by at least 90%) will be calculated by treatment groups of subjects with baseline PSA value with 1st line AAT and PSA measured at Week 13.

The response rate between the enzalutamide and flutamide groups will be compared using the stratified Cochran–Mantel–Haenszel test. The stratification factor will be the disease stages (M0/N0, M0/N1, or M1) used as stratification factor for allocation.

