5.1 Intent-to-Treat (ITT)

Intent-to-Treat (ITT) population is defined as all subjects randomized in this study. The ITT population will be analyzed by randomized treatment group (treatment group based on randomization). Efficacy analyses will be done in the ITT population.

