7.4 Analysis of Efficacy

All analysis of efficacy will be presented by planned treatment group for ITT population, unless specified otherwise. The data obtained at Day 1 visit will be used as the baseline for efficacy assessment except for rPFS for which the data at the Screening visit will be used as the baseline.

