The PSA response rate decreasing by at least 50% (or by at least 90%) will be calculated by treatment groups of subjects with baseline PSA value with 1st line AAT and PSA measured at week 13. The PSA response rate at week 13 will be assessed by the same method as that with the PSA response rate to 1st line AAT. Water fall plot will be made to present the percent change of PSA from baseline at Week 13 PSA value for each patient.

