7.11.1 Missing Data

As a general principle, no imputation of missing data will be done. Exceptions are the start and stop dates of concomitant medication and radiotherapy for prostate cancer. The imputed dates will be used to determining whether a medication or radiotherapy is prior to/on or after the first dose of study drug. The following rules will be applied to impute partial dates for medications and radiotherapy for prostate cancer:

If start date of a medication/radiotherapy is partially missing, impute as follows:

- If both Month and Day are missing, then set to January 1
- If only Day is missing, then set to the first day of the month

If end date of a medication/radiotherapy is partially missing, impute as follows:

- If both Month and Day are missing, then set to December 31
- If only Day is missing, then set to last day of the month

If start date and/or end date of a medication/radiotherapy is completely missing, do not impute.

Listings will present the actual partial dates; imputed dates will not be shown.

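### The Week-13 PSA response rate is tested only in subjects with a Week-13 PSA, a subset formed after randomization, although the protocol interprets its tests on the ITT

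*SAP*

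**What the plan says.** The Week-13 response rate is a secondary endpoint. SAP 7.4.2.3 states that it "will be calculated by treatment groups of subjects with baseline PSA value with 1st line AAT and PSA measured at week 13". Protocol 7.4.2.3 has the same restriction, "subjects with baseline PSA value with 1st line AAT and PSA measured at Week 13", and so does the protocol synopsis.

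The endpoint is tested. According to SAP 7.4.2.3, "The PSA response rate at week 13 will be assessed by the same method" as the overall first-line response, which in SAP 7.4.2.2 means a stratified Cochran–Mantel–Haenszel test and a Mantel–Haenszel risk difference with its 95% confidence interval. SAP 7.1.1 makes comparisons two-sided at 0.05.

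On the population, protocol 7.4 states: "The interpretation of results from statistical tests will be based on the ITT". SAP 5.1 states: "Intent-to-Treat (ITT) population is defined as all subjects randomized in this study". SAP 7.4 adds an exception clause: "All analysis of efficacy will be presented by planned treatment group for ITT population, unless specified otherwise".

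On missing values, SAP 7.11.1 states: "As a general principle, no imputation of missing data will be done". Its exceptions concern dates only. Neither document has a rule that counts a missing Week-13 PSA as non-response, or a sensitivity analysis for it.

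**The concern.** A Week-13 PSA is a post-randomization fact, and treatment can influence whether it exists. A comparison limited to subjects who have one sets two selected subsets against each other, so randomization no longer protects the test or the risk difference.

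The schedule makes the loss systematic. The Schedule of Assessments places PSA at Day 1 and then at Week 13, while safety laboratory tests also fall at Weeks 5 and 9. A drug-specific discontinuation criterion in protocol 6.1, such as the liver criterion for flutamide or the seizure criterion for enzalutamide, can therefore take a subject off the first drug before any scheduled post-baseline PSA. Such a subject is normally absent from both numerator and denominator. The size, and possibly the significance, of a tested secondary comparison is at stake.

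**Working it through.** **1. Who is lost.** The Week-13 window is Day 85 ± 7 (SAP 7.11.3), that is, Day 78 to Day 92. Protocol 7.10 excludes values outside the acceptable range. A subject who leaves the first drug before about Day 78 normally has no qualifying value. The second drug is to start within 6 weeks (protocol 2.2.1), so a PSA near Day 85 may already belong to the second line. The SAP does not say whether an in-window value taken after stopping the first drug would count.

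**2. Figures available.** The documents plan for TTPP1 only (135 events, 74 per group before dropout, 100 per group enrolled). They state no Week-13 response rate and no Week-13 missing proportion, so there is no plan figure to reproduce. The approximately 25% dropout is for the whole study.

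**3. Size of the distortion in one arm.** Let m be the proportion missing, p the rate among those measured and q the unknown rate among those missing. The all-randomized rate is (1 − m)p + mq. The measured-only rate exceeds it by m(p − q), which is positive only if q < p. The bias in the treatment difference is this quantity for enzalutamide minus the same quantity for flutamide.

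**4. Illustration.** The assumptions are 100 randomized per arm, 60 responders on enzalutamide, 25 on flutamide, and q = 0.

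| Missing (enzalutamide, flutamide) | Enzalutamide | Flutamide | Difference |
|---|---|---|---|
| None, or all randomized | 60/100 = 60.0% | 25/100 = 25.0% | 35.0 points |
| 15 and 5 | 60/85 = 70.6% | 25/95 = 26.3% | 44.3 points |
| 5 and 20 | 60/95 = 63.2% | 25/80 = 31.3% | 31.9 points |

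The formula agrees. For 15 and 5 missing, 0.15 × 70.6 − 0.05 × 26.3 = +9.3 points. For 5 and 20 missing, 0.05 × 63.2 − 0.20 × 31.25 = −3.1 points. The three differences give unstratified pooled z of about 5.0, 5.9 and 4.2, so the test conclusion is the same in all three.

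**5. When the conclusion could move.** Take a smaller assumed effect, 45 v 30 responders per 100, again with q = 0 and an unstratified pooled z-test. All randomized: 15.0 points, p = 0.029. With 5 and 15 missing: 45/95 − 30/85 = 47.4% − 35.3% = 12.1 points, p = 0.10. With 15 and 5 missing: 45/85 − 30/95 = 52.9% − 31.6% = 21.4 points, p = 0.004.

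**6. Error rate with no true difference.** With equal all-randomized response, 5 and 15 missing per 100, and q = 0, the nominal 5% test rejects about 8% of the time at a 30% response rate and about 13% at 50%.

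**The case against.** The restriction is open and prespecified. It stands in the synopsis, the protocol section and the SAP alike, and the exception clause in SAP 7.4 allows it. Within the SAP it is a disclosed measured-only analysis. That stands, but protocol 7.4 has no such clause, so the conflict there remains.

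Early stops are also visible elsewhere. TTF1 counts every first-line discontinuation as an event, and SAP 7.2.1 tabulates first-line discontinuation by primary reason and visit participation by group. This is true and useful, but it does not return these subjects to the Week-13 rate or its test.

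A reader might infer four stronger things, none of which the documents support:

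- *Every early stopper is a failure on this endpoint.* The endpoint measures PSA change. A subject who stopped for raised transaminases or a seizure is not thereby a PSA non-responder, and some values will be missing only through a missed or out-of-window visit. Overstatement requires that missing subjects respond less often than measured ones.
- *The rule favours enzalutamide.* The protocol's package-insert excerpts list seizure at 0.2% for enzalutamide, and AST and ALT increases at 13.2% each for flutamide (increases of any size, not those meeting the discontinuation criterion). If liver events dominate, flutamide may lose more subjects and the rule could work against enzalutamide. The direction cannot be fixed.
- *Early progression is an equal route to loss.* No PSA or imaging is scheduled between Day 1 and Week 13, so earlier progression would be found only clinically or at an unscheduled visit. Toxicity is the clearer route.
- *The result would be overturned.* On 60 v 25 responders the estimate moves but the conclusion does not. A change of significance needs a smaller effect, such as the assumed 45 v 30.

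**Conclusion.** The point holds as a weakness in one tested secondary endpoint. Both documents compute and test Week-13 response in a post-randomization subset, which does not fit the protocol's statement that tests are interpreted on the ITT. Nothing else in the plan repairs the comparison.

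If missing subjects respond less often than measured ones, the rates are overstated. The difference is then biased in a direction that depends mainly on which arm loses more subjects, and the documents do not give this. On the assumed 60 v 25 responders per 100, with every missing subject a non-responder, the shift runs from about −3 to +9 points for the two missing patterns shown. All of these counts are assumptions. The primary TTPP1 analysis does not use this denominator and is unaffected.

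**What to change.** In SAP 7.4.2.3, compute Week-13 PSA50 and PSA90 with all randomized subjects who have a baseline PSA as the denominator, and count a missing Week-13 PSA as non-response. Report the prespecified measured-only rate alongside it as a sensitivity analysis. Tabulate missing Week-13 PSA by arm and reason, keeping early discontinuation apart from missed or out-of-window visits. State whether an in-window PSA taken after the first drug was stopped counts.

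Align the synopsis, protocol 7.4.2.3 and SAP 7.4.2.3. Because the SAP is dated 8 July 2020 as final, the alternative is to justify the change in the clinical study report, as SAP section 1 requires.

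No new PSA data are needed. The cost is a short text change, one rerun and one table. Reported rates become slightly lower, and subjects whose value is missing only because of a missed or out-of-window visit count as non-responders. Showing both rates lets the reader judge how much that matters.

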7.4.2.4 Time to PSA Decrease by 50% from Baseline with 1st Line AAT

The time to PSA decrease by 50% with 1st line AAT is defined as the period from randomization to the day when the decrease of PSA from baseline by 50% is first identified. Convention of censoring is specified in Table 7-1.

The benefit of enzalutamide as compared to flutamide will be assessed with the stratified log-rank test as the primary efficacy analysis. The stratification factor will be the disease stages (M0/N0, M0/N1, or M1) used as stratification factor for allocation.

The distribution of the time to PSA decrease by 50% with 1st line AAT will be estimated using the Kaplan–Meier method. The median time to PSA decrease by 50% will be estimated using the 50 percentile value of the Kaplan–Meier curve. The two-sided 95% CI will be calculated based on the estimation.

7.4.2.5 Time to Treatment Failure of 1st Line AAT (TTF1)

TTF1 is defined as the period from randomization to the date of discontinuation of 1st line AAT. Convention of censoring is specified in Table7-1.

TTF1 will be assessed using the same method as that with time to PSA decrease by 50% from baseline with 1st Line AAT.

7.4.2.6 Time to Treatment Failure of 2nd Line AAT (TTF2)

TTF2 is defined as the period from randomization to the date of discontinuation of 2nd line AAT. Convention of censoring is specified in Table 7-1.

The distribution of the time to treatment failure of 2nd line AAT will be estimated using the Kaplan–Meier method. The median time to treatment failure of 2nd line AAT will be estimated using the 50 percentile value of the Kaplan–Meier curve. The two-sided 95% CI will be calculated based on the estimation.

7.4.2.7 Radiographic Progression-Free Survival (rPFS)

The rPFS is defined as the time from randomization to the first objective evidence of radiographic disease progression assessed by the blinded independent central review facility or on-study death, defined as death within 28 days after treatment discontinuation, whichever occurs first. rPFS will be assessed in the ITT population. Radiographic disease progression will include soft tissue disease progression and confirmed bone disease progression. The censoring rules are shown in Table 7-1. The analysis of rPFS will be presented by planned treatment group for subjects that having least one distant metastasis at baseline in ITT population.

rPFS will be assessed using the same method as that with TTPP1. i.e. Stratified log-rank test and unstratified cox regression will be applied to rPFS and estimate the distribution using Kaplan-Meier method.

7.4.3 Analysis of Exploratory Endpoints

7.4.3.1 Time to PSA Progression with 2nd Line AAT (2nd TTPP)

2nd TTPP is defined as the period from the start of 2nd line AAT to the first day when PSA progression is objectively identified. Convention of censoring is specified in Table 7-1.

The 2nd TTPP will be assessed by the same method as that with the Time to Treatment Failure of 2nd Line AAT (TTF2).

7.4.3.2 PSA Response Rate to 2nd line AAT (Decrease by at Least 50% or 90% from Baseline)

The PSA response rate to 2nd line AAT decreasing by at least 50% (or by at least 90%) will be calculated by treatment groups of subjects with baseline PSA value and PSA measured at least once at least 3 weeks passed after the lowest PSA. The PSA response rate to 2nd line AAT will be assessed by the same method as that with the PSA response rate to 1st line AAT.

Water fall plot will be made to present the percent change of PSA from baseline at the lowest PSA value (except within 3 weeks from baseline) for patient who have at least one time point PSA reduction in the 2nd line AAT period, and the highest PSA value (except within 3 weeks from baseline) for patient who have never had PSA reduction, respectively.

7.4.3.3 Metastasis-Free Survival (MFS)

MFS is defined as the period from randomization to new radiographic metastatic lesion or death of any cause during the study period, whichever occurs earlier. Evaluation will be made in subjects in whom distant metastasis is not confirmed at baseline. MFS will be

assessed by the same method as that with the Time to Treatment Failure of 2nd Line AAT (TTF2).

7.4.3.4 Functional Assessment of Cancer Therapy–Prostate (FACT-P) with 1st Line AAT and 2nd Line AAT

The FACT-P domain scores and total score and their change from baseline will be summarized by treatment group as randomized for the ITT population. These measurement values and changes from baseline will be plotted as mean +/- SD plot. The FACT-P domain score and total score will be calculated using the Manual of Functional Assessment of Chronic Illness Therapy (FACIT) Measurement System.

7.4.3.5 European Quality of Life-5 Dimension-5 Level Instruments (EQ-5D-5L) with 1st Line AAT and 2nd Line AAT

Following analysis will be applied for the ITT population. The subjects' current health state is assessed using a visual analogue scale form 0 (worst imaginable health state) to 100 (best imaginable health state). The current health state score will be summarized by visit and treatment group. QOL utility index will be derived according to section 6.1.4 will also be summarized by visit and treatment group. These measurement values will be plotted as mean +/- SD plot. Additionally, a within-subject change will be calculated per visit as the post-baseline measurement minus the baseline measurement and summarized by visit and treatment group in the same way.

7.4.3.6 Brief Pain Inventory-Short Form (BPI-SF) with 1st Line AAT and 2nd Line AAT

Descriptive statistics for Pain severity and Pain Interference and their change from baseline will be summarize by visit and treatment group for the ITT population. These measurement values and changes from baseline will be plotted as mean +/- SD plot.

7.4.3.7 Brief Fatigue Inventory (BFI) with 1st Line AAT and 2nd Line AAT

Descriptive statistics for global fatigue score and its change from baseline will be summarize by visit and treatment group for the ITT population. These measurement values and changes from baseline will be plotted as mean +/- SD plot.

Global fatigue score will be categorized according to the following categories by treatment group:

- Mild: global fatigue score be in range from 1 to 3.
- Moderate : global fatigue score be in range from 4 to 6.
- Severe : global fatigue score be in range from 7 to 10.

Counts and percentages of subjects in each of these categories will be summarized for each treatment group.

7.4.3.8 Objective Response Rate (ORR) in best Overall Soft Tissue Response of RECIST Guidelines with 1st Line AAT

For the comparison of ORR between the enzalutamide and flutamide groups, the stratified Cochran–Mantel–Haenszel test will be used. The stratification factor will be the disease stages (M0/N0, M0/N1, or M1) used as stratification factor for allocation.

ORR, its Clopper-Pearson exact confidence interval and its count within stratification will be summarized for each treatment. Mantel-Haenszel common risk difference for response (enzalutamide - /flutamide) and its 95% confidence interval based on the variance claimed by Sato (1989) will be estimated. And count and percentage of overall soft tissue response which is assessment using RECIST 1.1 will be tabulated. The summarized category is shown as follows:

- Complete response (CR)
- Partial response (PR)
- Progressive disease (PD)
- Stable disease (SD)
- Non-evaluable (NE)

Table 7-1: Definition of time to event and censor

	TTPP1	TTPP2	2nd TTPP	Time to PSA 50%/90% decline	TTF1	TTF2	rPFS	MFS
Subjects without PSA value at baseline or in observation period	Considered as censoring at randomization	Considered as censoring at randomization	Excluded from analysis	Considered as censoring at randomization	Not considered as censoring *To be judged based on continuation of study treatment	Not considered as censoring *To be judged based on continuation of study treatment	Not considered as censoring *To be judged based on result of radiographic assessment	Not considered as censoring *To be judged based on result of radiographic assessment
Subjects without the result of radiographic assessment at baseline or in observation period	Not considered as censoring *To be judged based on result of PSA measurement	Not considered as censoring *To be judged based on result of PSA measurement	Not considered as censoring *To be judged based on result of PSA measurement	Not considered as censoring *To be judged based on result of PSA measurement	Not considered as censoring *To be judged based on continuation of study treatment	Not considered as censoring *To be judged based on continuation of study treatment	Considered as censoring at randomization	Considered as censoring at randomization
Subjects without PSA progression at final data cut-off (Including cases inconsistent with PSA progression defined by the protocol)	Subjects who continue the first study drug are considered as censoring at final PSA measurement	Considered as censoring at final PSA measurement	Subjects who continue the first study drug are excluded from analysis Subjects who have shifted to the second study drug are considered as censoring at final PSA measurement	Considered as censoring at final PSA measurement	Not considered as censoring *To be judged based on continuation of study treatment	Not considered as censoring *To be judged based on continuation of study treatment	Not considered as censoring *To be judged based on result of radiographic assessment	Not considered as censoring *To be judged based on result of radiographic assessment

Subjects without radiographic progression at final data cut-off (Including cases inconsistent with progression defined by the protocol)	Not considered as censoring *To be judged based on result of PSA measurement	Not considered as censoring *To be judged based on result of PSA measurement	Not considered as censoring *To be judged based on result of PSA measurement	Not considered as censoring *To be judged based on result of PSA measurement	Not considered as censoring *To be judged based on continuation of study treatment	Not considered as censoring *To be judged based on continuation of study treatment	Considered as censoring at final radiographic assessment	Considered as censoring at final radiographic assessment
Death during the study	Subjects who died during treatment with the first study drug are considered as censoring at final PSA measurement before death	Considered as censoring at final PSA measurement before death	Subjects who died during treatment with the first study drug are excluded from analysis Subjects who died during treatment with the second study drug are considered as censoring at final PSA measurement before death	Considered as censoring at final PSA measurement before death	The event is considered to occur at the time of death	The event is considered to occur at the time of death	The event is considered to occur at the time of death	The event is considered to occur at the time of death
Subjects who discontinued treatment during the study	Subjects who discontinue the first study drug are considered as censoring at final PSA measurement before discontinuation	Considered as censoring at final PSA measurement before discontinuation	Subjects who discontinue the first study drug are excluded from analysis Subjects who discontinue the second study drug are considered as censoring at final PSA measurement before discontinuation	Considered as censoring at final PSA measurement before discontinuation	The event is considered to occur at the time of discontinuation	The event is considered to occur at the time of discontinuation	Considered as censoring at final radiographic assessment before discontinuation	Considered as censoring at final radiographic assessment before discontinuation

Subjects who used prohibited concomitant medication or therapy during the study	Subjects who use one with the first study drug are considered as censoring at final PSA measurement before use	Considered as censoring at final PSA measurement before use	Subjects who use one with the first study drug are excluded from analysis Subjects who use one with the second study drug are considered as censoring at final PSA measurement before use	Considered as censoring at final PSA measurement before use	Not considered as censoring *To be judged based on continuation of study treatment	Not considered as censoring *To be judged based on continuation of study treatment	Considered as censoring at final radiographic assessment before use	Considered as censoring at final radiographic assessment before use
Subjects who miss PSA data at least twice consecutively at scheduled PSA measurement points	Considered as censoring at final PSA measurement before missing data occur	Considered as censoring at final PSA measurement before missing data occur	Subjects who continue the first study drug are excluded from analysis Subjects who have shifted to the second study drug are considered as censoring at final PSA measurement before missing data occur	Considered as censoring at final PSA measurement before missing data occur	Not considered as censoring *To be judged based on continuation of study treatment	Not considered as censoring *To be judged based on continuation of study treatment	Not considered as censoring *To be judged based on result of radiographic assessment	Not considered as censoring *To be judged based on result of radiographic assessment
Subjects who miss radiographic assessment at least twice consecutively at scheduled radiographic assessment points	Not considered as censoring *To be judged based on result of PSA measurement	Not considered as censoring *To be judged based on result of PSA measurement	Not considered as censoring *To be judged based on result of PSA measurement	Not considered as censoring *To be judged based on result of PSA measurement	Not considered as censoring *To be judged based on continuation of study treatment	Not considered as censoring *To be judged based on continuation of study treatment	Considered as censoring at final radiographic assessment before missing data occur	Considered as censoring at final radiographic assessment before missing data occur

Sponsor: Astellas Pharma Inc. SAP Version 1.00

ISN/Protocol 9785-MA-3051

7.4.4 **Analysis of Other Variables**

PSA measurement

Descriptive statistics for PSA measurement and its change from baseline will be summarized at by visit and treatment group. These measurement value and change from baseline will be plotted as mean +/- SD plot.

Swimmer's plot

Swimmer's plot will be made to present treatment flow and event occurrence for each patient. This plot will include time on and off of the 1st/2nd line AAT continuations as a bar chart, and the points at which drug related AEs (by CTCAE grades), PSA progression, radiographic progression, PSA response, and death.

7.5 **Analysis of Safety**

All analysis of safety will be presented by actual treatment group for SAF, unless specified otherwise. The last non-missing measurement prior to the first dose of study drug will be used as the baseline.

7.5.1 **Adverse Events**

The severity of all AEs is to be evaluated by the investigator based on the National Cancer Institute's CTCAE version 4.0. The coding dictionary for this study will be Medical Dictionary for Regulatory Activities (MedDRA) version 19.1. It will be used to summarize AEs by SOC and PT.

The safety analysis will be performed in the safety analysis set, and summarized by the time of assessment and by the treatment group that actually received the study drugs. The period of onset in the treatment period with the study drug is defined up to 28 days after the final treatment with the study drug, start date of cytocidal chemotherapy, or start date of new treatment for prostate cancer, whichever occurs first. Safety will be assessed by AEs, frequency of treatment discontinuation associated with AEs, and laboratory test value summary statistics. Descriptive statistics, and not inferential statistics, will be used.

The total number of AEs reported will be presented by treatment arm (i.e. enzalutamide v.s. flutamide) and overall total for the SAF. The same analysis will be provided dividing treatment lines. AEs which have occurred during 1st line AAT and 2nd line AAT will be included to analysis. In this 'event level' analyses, all AEs will be counted separately. The following categories will be presented:

- Number of AEs,
- Number of AEs leading to study drug discontinuation,
- Number of drug-related AEs,
- Number of drug-related AEs leading to study drug discontinuation,
- Number of grade 3 or higher AEs,
- Number of grade 3 or higher drug-related AEs,
- Number of serious adverse events (SAEs),

- Number of drug-related SAEs,
- Number of SAEs leading to study drug discontinuation,
- Number of drug-related SAEs leading to study drug discontinuation,
- Number of SAEs leading to death,
- Number of drug-related SAEs leading to death.

The number and percentage of subjects experiencing AEs will be presented by treatment arm and overall total for the SAF. The same analysis will be provided dividing treatment lines. AEs which have occurred during 1st line AAT and 2nd line AAT will be included to analysis. In this 'subject level' analyses, multiple AEs within the same category for a particular subject will only be counted once and the denominator for the percentage calculation will be the number of subjects in the SAF. The following categories will be presented:

- Number and percentage of subjects with AEs,
- Number and percentage of subjects with AEs leading to study drug discontinuation,
- Number and percentage of subjects with drug-related AEs,
- Number and percentage of subjects with drug-related AEs leading to study drug discontinuation,
- Number and percentage of subjects with grade 3 or higher AEs,
- Number of grade 3 or higher drug-related AEs,
- Number and percentage of subjects with SAEs,
- Number and percentage of subjects with drug-related SAEs,
- Number and percentage of subjects with SAEs leading to study drug discontinuation,
- Number and percentage of subjects with drug-related SAEs leading to study drug discontinuation,
- Number and percentage of subjects with SAEs leading to death,
- Number and percentage of subjects with drug-related SAEs leading to death.

The number and percentage of subjects experiencing AEs will be tabulated by SOC, PT, treatment arm and overall total for the SAF. The same analysis will be provided dividing treatment lines. AEs which have occurred during 1st line AAT and 2nd line AAT will be included to analysis. For this and similar analyses, an AE will only be counted once for each subject if the same AE is experienced on more than one occasion. Tables will be sorted by descending overall total of SOC and PT frequency. The following summaries will be produced:

- AEs,
- AEs leading to study drug discontinuation,
- drug-related AEs,
- drug-related AEs leading to study drug discontinuation,
- grade 3 or higher AEs,
- SAEs,

- drug-related SAEs,
- SAEs leading to study drug discontinuation,
- drug-related SAEs leading to study drug discontinuation,
- SAEs leading to death,
- drug-related SAEs leading to death,
- TEAEs excluding serious adverse events that equal to or exceed a threshold of 2.0% in any treatment group, and
- Common TEAEs that equal to or exceed a threshold of 2.0% in any treatment group.

The number and percentage of subjects experiencing AEs will be tabulated by SOC, PT, maximum severity, treatment arm and overall total for the SAF. The same analysis will be provided dividing treatment lines. AEs which have occurred during 1st line AAT and 2nd line AAT will be included to analysis. For this and similar analyses, a subject reporting the same adverse event more than once is counted once at the maximum severity when calculating incidence. Tables will be sorted by descending overall total of SOC and PT frequency. The following summaries will be produced:

- AEs,
- drug-related AEs,
- SAEs,

The listing for subjects those who meet the special situations such as overdose, drug abuse, inadvertent or accidental exposure, or medication error will be prepared.

